7.4 Subgroup analyses

No subgroup analyses are planned.

7.5 Deviations from planned analysis

Should any additional statistical analyses be required during the final analysis, appropriate methods will be used, and any changes, including the rationale for use, will be documented in the clinical study report or manuscript.

7.6 Safety data

Safety data (adverse events reported from time of first exposure to treatment to end of treatment) will be summarised by group. Any serious adverse events will be described in full including possible relationship to the treatment.

Serious adverse events related or unrelated to the intervention, will be analysed using a logistic regression model with the random effects, pre-specified prognostic variables and treatment group as explanatory variables.

8. Description of Tables and Figures

All data up to the time of study completion/withdrawal from the study will be included in the analysis, regardless of duration of treatment.

All raw data will be presented to the original number of decimal places. The mean and standard deviation will be presented with to 2 decimal places or 3 significant figures depending upon the nature of the data. Percentages will be presented in to 1 decimal place. All categories of variables will be presented even if there is no data. Blank cells, were data are not expected, will be filled by "-" in reporting of results.

Precision of p-values will be 3 decimal places, i.e. p-values less than 0.001 will be presented as <0.001 and if equal to 1 then \ge 0.999.

9. Software

All analysis will be performed using SAS[®] Software version 9.4 and Stata version 17.

10. References

- 1. Collins, R. and N. Kishita, *Prevalence of depression and burden among informal caregivers of people with dementia: A meta-analysis.* Ageing and Society, 2020. **40**(11): p. 2355-2392.
- 2. Kaddour, L. and N. Kishita, *Anxiety in informal dementia caregivers: a meta-analysis of prevalence.* Journal of Geriatric Psychiatry and Neurology, 2020. **33**(3): p. 161-172.
- 3. McManus, S., et al., eds. *Mental health and wellbeing in England: Adult psychiatric morbidity survey 2014*. 2016, NHS Digital: Leeds, UK.
- 4. National Institute for Health and Care Excellence, *NICE guideline [NG97] Dementia: assessment, management and support for people living with dementia and their carers*. 2018, NICE: London, UK.
- 5. Alzheimer's Society, *Dementia 2014: Opportunity for change*. 2014, Alzheimer's Society: London, UK.
- 6. A-Tjak, J.G.L., et al., A meta-analysis of the efficacy of acceptance and commitment therapy for clinically relevant mental and physical health problems. Psychotherapy and Psychosomatics, 2015. **84**(1): p. 30-36.

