6.11.3 Data Monitoring for Harm

6.11.3.1 Safety reporting

Definitions of harm of the EU Directive 2001/20/EC Article 2 based on the principles of ICH GCP apply to this trial.

This is a low-risk intervention. No specific risks, or adverse events were reported during feasibility testing of the intervention[22]. Any non-serious untoward incidents occurring during this trial (e.g. clear evidence of high levels of distress making participants difficult to continue with the study) will be recorded in an incident report form which will be monitored for frequency and severity. The participant's GP will also be informed to contact NCTU if they become aware of any adverse event during the study such as significant deterioration in mental health and they feel that the participant should no longer be taking part in the study. Serious adverse events (SAE) will be collected using an SAE form.

Table 3: Serious Adverse Event Definitions

Serious Adverse Event (SAE)	Any adverse event that:
	 results in death; is life threatening*; requires hospitalisation or prolongs existing hospitalisation**; results in persistent or significant disability or incapacity.
	The most likely SAE to occur in this study is new reports of active suicidal ideation with active suicidal behaviours/plans and imminent intent.

* The term life threatening here refers to an event in which the patient is at risk of death at the time of the event; it does not refer to an event that might hypothetically cause death if it was more severe (e.g. a silent myocardial infarction).

** Hospitalisation is defined as an in-patient admission, regardless of length of stay, even if the hospitalisation is a precautionary measure for continued observation. Hospitalisation for preexisting conditions (including elective procedures that have not worsened) do not constitute an SAE.

Serious adverse events do NOT include:

- Pre-existing disease or a physical health condition present before trial treatment;
- An exacerbation of such pre-existing physical illness (e.g. cancer) during the trial;
- A physical health condition that is detected after trial treatment.

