6.11.3.5.1 Seriousness assessment

When an AE occurs, the individual responsible for the care of the participant (Research Associate or trial therapist) must first assess whether or not the event is serious in conjunction with the Chief Investigator (if AE is identified by Research Associate) or the Principal Investigator (if AE is identified by trial therapist) using the definition given in Table 3. If the event is classified as 'serious' then an SAE form must be completed, and the Trial Manager notified within one working day.

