6.11.3.6 Notifications

6.11.3.6.1 Notifications by the Investigator to NCTU

NCTU must be notified of all SAEs within one working day of a responsible individual (Research Associate or trial therapist) becoming aware of the event. The responsible individual should notify NCTU of any SAEs occurring from the time of randomisation until the last follow-up assessment.

The SAE form must be completed by the responsible individual (Research Associate or trial therapist) with attention paid to the causality and expectedness of the event. The responsible investigator (the Chief Investigator for Research Associates and the Principal Investigator for trial therapists) should check the SAE form at the earliest opportunity, make any changes necessary, sign and then email to the Trial Manager at NCTU within one working day for review.

The Trial Manager will review the SAE form and disseminate to the Chief Investigator and sponsor representative within 72 hours of being informed to assess relatedness. The Trial Manager will enter the report into the database. The DMEC will be informed of SAEs by the Trial Manager periodically unless the Chief Investigator or sponsor representative escalates the SAE or deems necessary. This is a non-CTIMP study and only SAEs that are related and unexpected will be reported to REC within 15 days of the Chief Investigator becoming aware of the event.

The minimum criteria required for reporting an SAE are the trial number and date of birth, name of reporting investigator and sufficient information on the event to confirm seriousness. Any further information regarding the event that is unavailable at the time of the first report should be sent as soon as it becomes available.

Follow-up SAE forms (clearly marked as follow-up) should be completed and emailed to NCTU, as per above procedure. Additional information and/or copies of test results etc may be provided separately. The participant must be identified by trial number, date of birth and initials only. The participant's name should not be used on any correspondence and should not be used on any correspondence.

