4.3 Sample size

Participants in our feasibility study had an average reduction of 26% on GAD-7. A reduction of 20% on GAD-7 is considered to be a Minimum Clinically Important Difference [13]. Using a conservative reduction of 20% from the mean baseline GAD-7 score, and using the variability estimated from our feasibility study, a clinically-meaningful effect size is estimated to be d = 0.55 for our sample. Recent systematic reviews of RCTs of self-help ACT and mindfulness-based interventions (mainly for individuals with a mental or physical health condition) demonstrated a pooled effect size of d = 0.35 for anxiety [14, 15]. One of these reviews, which solely focused on RCTs of self-help ACT [14] demonstrated that when analysis was limited to studies that utilised guided self-help ACT, the pooled effect size increased to d = 0.61, while limiting analysis to studies that used an unguided approach decreased the pooled effect size to d = 0.16. The effect size calculated from our feasibility study of iACT4CARERS, which utilised a guided approach, is in line with the effect size reported in previous reviews.

To ensure adequate statistical power, we have decided to take the most conservative approach possible and have used an effect size of d = 0.35 in our sample size calculation. To detect the effect size of d = 0.35between the two trial arms at a two-tailed significant level of 5% with 90% statistical power, each arm requires 173 participants (i.e. 346 in total). Twenty seven percent of carers were lost to follow-up in our feasibility study. Assuming a dropout rate of 30%, a total of 496 carers will be recruited over 20 months (i.e. 24.8 participants per month).

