7.1 Outcome definitions

7.1.1 Primary outcome

The primary outcome is anxiety symptoms as assessed by the Generalized Anxiety Disorder-7 (GAD-7 [16]) at 12 weeks. In addition to the Mean (and SD), the proportions of participants falling into different severity ranges (mild, moderate, severe) at each time point will be reported.

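### The harm summary in SAP 7.6 rests on reported events, and no planned output counts individual worsening on GAD-7 or PHQ-9

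*SAP*

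**What the plan says.** - **What is summarised.** SAP 7.6: "Safety data (adverse events reported from time of first exposure to treatment to end of treatment) will be summarised by group". Serious events are also described in full and modelled by logistic regression.
- **How deterioration is picked up.** Protocol 6.11.3.1 asks the GP to contact the trials unit about "any adverse event during the study such as significant deterioration in mental health", where the GP also thinks that the carer should leave the study. Non-serious incidents "will be recorded in an incident report form which will be monitored for frequency and severity".
- **Who assesses events.** Protocol 6.11.3.5.1 says that "the individual responsible for the care of the participant (Research Associate or trial therapist) must first assess whether or not the event is serious". Protocol 6.4.2.2 rules out trial-therapist contact for control carers.
- **What is measured in everyone.** Protocol Table 2 schedules GAD-7 and PHQ-9 at baseline, 12 and 24 weeks.
- **How the scales are reported.** For GAD-7, SAP 7.1.1 says that "the proportions of participants falling into different severity ranges (mild, moderate, severe) at each time point will be reported". PHQ-9 has no equivalent. SAP 7.2 models both as scores.
- **Window for serious events.** Protocol 6.11.3.6.1 covers those "occurring from the time of randomisation until the last follow-up assessment".

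**The concern.** The protocol's own example of an adverse event is a marked decline in mental health. GAD-7 and PHQ-9 measure this on one schedule in both arms, yet the safety summary relies on spontaneous reports.

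The chance of a report is not the same in the two arms. Intervention carers write reflections that a therapist reads and are offered two calls. A control carer who completes follow-up online within a week triggers no chasing call (Protocol 6.6.1.2) and may have little direct contact with trial staff. A by-arm table of reports therefore partly measures the opportunity to report. This could inflate the intervention count relative to control, while worsening in either arm can pass unseen.

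At stake is whether the report can say how many carers worsened in each arm, alongside the mean effect.

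**Working it through.** **1. The plan's own size.** With d = 0.35, two-sided 5% and 90% power, n = 2 × (1.96 + 1.2816)² / 0.35² = 171.5, so 172 per arm. The t-based calculation gives 172.5, so 173. Then 173 / 0.70 = 247.1, so 248 per arm and 496 in total. The stated figures reproduce. At 30% loss, 248 − 173 = 75 carers per arm would have no follow-up score.

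**2. Totals per time point do not show individual worsening.** Take 173 carers in one arm. In case A nobody changes band. In case B 17 move from mild to moderate and 17 from moderate to mild. The severity proportions are identical, but the number who moved up is 0 in A and 17 in B.

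**3. The mean can hide a minority.** Suppose 10% of the intervention arm do worse than control by 0.55 SD and 90% do better by 0.45 SD. The overall benefit is 0.90 × 0.45 − 0.10 × 0.55 = 0.405 − 0.055 = 0.35 SD, exactly the design effect. This shows what is possible, not what is likely.

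**4. Precision of a comparison.** The documents give no worsening rate, so these rates are assumptions. Half-width = 1.96 × √[p₁(1−p₁)/173 + p₂(1−p₂)/173].

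| Assumed rates | Half-width, percentage points |
|---|---|
| 5% in both arms | 4.6 |
| 10% in both arms | 6.3 |
| 10% and 15% | 6.9–7.0 (SE 0.0355) |
| 20% in both arms | 8.4 |

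Excluding carers already severe at baseline shrinks the denominators and widens these intervals.

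**5. Order of magnitude.** Assume normal change scores, unit SD at both times, baseline-to-follow-up correlation ρ of 0.4 to 0.7, and mean change m on TAU of 0 to −0.3 SD. Count a rise of 0.55 SD, which is the size that SAP 4.3 equates to 20% of mean baseline. P(worse) = 1 − Φ[(0.55 − m)/√(2(1−ρ))].
- TAU: from 0.136 (ρ = 0.7, m = −0.3) to 0.308 (ρ = 0.4, m = 0), or 24 to 53 of 173.
- Intervention, with m lower by 0.35: from 0.061 to 0.206, or 10 to 36 of 173.

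Much of this is ordinary fluctuation, so only the contrast between arms is informative.

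**6. The windows side by side.** Treatment lasts 12 weeks and the last follow-up is at 24. Read literally, SAP 7.6 leaves out 24 − 12 = 12 weeks, half of follow-up, and gives TAU no defined first exposure. The protocol window for serious events runs from randomisation to the last follow-up. SAP section 8 separately includes all data to study completion, regardless of treatment duration.

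**The case against.** A reader might infer that the SAP ignores GAD-7 and PHQ-9 as evidence of harm, so that carers made worse go uncounted. The documents do not support that.
- SAP 7.1.1 reports GAD-7 bands at each time point. Allocation is minimised on baseline band, so an excess of severe carers in one arm would be visible.
- The mean models are two-sided and would show average harm on either scale.
- Deterioration that is reported is summarised by group, and incidents are monitored, although Protocol 6.11.3.5.2 says that severity is not graded.

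Nor does the SAP break a commitment. The protocol speaks of significant deterioration in an instruction to GPs, and neither document defines an adverse event by a score. The intervention is described as low-risk, with no adverse events in the feasibility study of 33 carers. At the design effect, step 5 has fewer carers worsening on the intervention than on TAU. Protocol 6.5.2 also calls the modified CSRI interview-based. If it is administered that way, control carers have more staff contact than Protocol 6.10.1, which treats all questionnaires as self-reported, suggests.

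It is also tempting to define worsening as a 20% rise from the carer's own baseline, since SAP 4.3 states: "A reduction of 20% on GAD-7 is considered to be a Minimum Clinically Important Difference". That statement concerns a reduction, and GAD-7 only. As a rule for worsening it fails at both ends:
- From the entry score of 5, a rise to 6 would count.
- From 18, 1.2 × 18 = 21.6 exceeds the maximum of 21, so carers at 18 or above could never count.
- A PHQ-9 of 0 has no percentage change, and from 23, 1.2 × 23 = 27.6 exceeds the maximum of 27.

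All of this stands, and it narrows the point. It does not supply a count of individual worsening.

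**Conclusion.** The point holds as a low-cost improvement. It does not affect the primary analysis. The harm summary depends on reporting, reporting opportunity differs by arm, and no planned output shows how many individual carers worsened. What goes unseen is unreported individual worsening that net proportions and means can cancel out.

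The difference in reporting is inferred from the planned contacts; the documents do not quantify it. The ±5 to ±8 point precision rests on 173 assessed per arm and on assumed rates. The comparison would be descriptive: both scales are self-reported by unblinded carers, and the 75 per arm who may be missing could outnumber those seen to worsen.

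The mismatch between the safety windows is separate, follows directly from the text, and must be reconciled.

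**What to change.** Add to SAP 7.6, by arm at 12 and 24 weeks:

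1. A GAD-7 band cross-table using the SAP Table 1 cut-offs: three baseline bands (entry requires 5 or above) by four follow-up bands, including minimal. Give the number and percentage who moved up at least one band among those not severe at baseline, the risk difference with 95% CI, and the number not assessed.
2. The distribution of individual change scores on GAD-7 and PHQ-9. This needs no threshold and shows worsening within the severe band. It also offsets the weakness of the bands, where 9 to 10 counts as a move and 10 to 14 does not.

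Label both a descriptive harm summary with no significance claim. State that TAU calibrates natural fluctuation and that carers were unblinded.

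Reconcile the safety window in SAP 7.6 with Protocol 6.11.3.6.1 and SAP section 8, including when the window starts for TAU.

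The cost is a paragraph of SAP text and two outputs from data already collected, with no added burden on carers. The main risk is over-reading ordinary fluctuation as harm, which the labelling and the control arm limit.

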6.4.2.2 Treatment Schedule

Participants will continue to receive any routine support over 12 weeks. They will receive no contact with trial therapists as described in ARM A.

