6.5.2 Secondary Outcomes

Clinical outcome measures

- Patient Health Questionnaire-9 (PHQ9[33]): A 9-item self-report questionnaire assessing the severity of depressive symptoms. Both GAD7 and PHQ9 are used routinely in NHS psychological services for assessing recovery.
- Comprehensive Assessment of Acceptance and Commitment Therapy processes (CompACT[34]): A 23-item self-report questionnaire assessing psychological flexibility, which is commonly used in ACT studies.
- Experiential Avoidance in Caregiving Questionnaire (EACQ[35]): A 15-item self-report questionnaire assessing experiential avoidance (one component of psychological flexibility) in the caregiving context.
- Serious adverse events related or unrelated to the intervention: Any serious adverse events reported during the trial will be recorded.
- Satisfaction With Therapy and Therapist Scale-Revised (STTS-R[36]): A 12-item self-report questionnaire assessing satisfaction with therapy and satisfaction with the therapist.

Cost-effectiveness measures

- EQ-5D-5L[37]): A 5-item self-report questionnaire assessing health-related quality of life.
- ICEpop CAPability measure for Older people (ICECAP-O[38]): A 5-item questionnaire assessing capabilities that are required to have a high quality of life in older adults.
- Modified Client Service Receipt Inventory (modified CSRI[31]): An interview-based measure of health and social care service utilisation. This scale will be used to monitor TAU received in both arms during the trial and to calculate patient costs.

Measures of bias

Expectations about treatment and participants' intervention arm preference are potential sources of bias that can affect treatment outcomes. These measures will be collected during the baseline session prior to randomisation, after participants are given a rationale for iACT4CARERS.

- Expectations about treatment: Two questions asking how much participants expect their symptoms and life to improve if they receive iACT4CARERS will be used (collected on a five-point Likert scale from 0 to 4).
- Treatment preference: Two questions asking how much they hope to receive iACT4CARERS and TAU alone without iACT4CARERS will be used (collected on a five-point Likert scale from 0 to 4).

Intervention fidelity measures

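### The SAP's safety window (first exposure to end of treatment) conflicts with the protocol's SAE window and with SAP section 8, is undefined for usual care, and read literally omits at least half of the 24-week period

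*SAP*

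**What the plan says.** **SAP 7.6** makes three statements.
- Safety data, defined as "adverse events reported from time of first exposure to treatment to end of treatment", are summarised by group.
- "Any serious adverse events will be described in full including possible relationship to the treatment". No window is given.
- SAEs "will be analysed using a logistic regression model with the random effects, pre-specified prognostic variables and treatment group as explanatory variables". Again no window is given.

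The SAP does not define first exposure or end of treatment for either arm. **SAP section 8** then sets a general rule that data up to completion of, or withdrawal from, the study enter the analysis however long treatment lasted. **SAP 5.2** analyses participants as randomised.

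**The protocol** frames safety by the trial period.
- 6.11.3.6.1: "The responsible individual should notify NCTU of any SAEs occurring from the time of randomisation until the last follow-up assessment".
- 6.5.2 lists SAEs among the secondary clinical outcomes: "Any serious adverse events reported during the trial will be recorded".
- 6.11.3.1 covers "Any non-serious untoward incidents occurring during this trial".

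**On treatment**, Protocol 6.4.1.2 gives eight online sessions within 12 weeks, each released five days after the last is completed, and then closes access. Protocol 6.4.2 describes the control as continuing routine support, with a nominal 12-week schedule. Of control participants it says: "They will receive no contact with trial therapists as described in ARM A". Protocol 6.4.5 lists an adverse event among the reasons treatment may stop early, and keeps such participants in follow-up.

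**The concern.** An on-treatment safety window suits a trial in which both arms start and stop something identifiable. Here only one arm does. Usual care has no start event, and an intervention participant who never opens a session has no exposure at all, although the analysis is by allocation.

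Three things are at stake.
- Events after programme access closes, such as a deterioration in weeks 12–24, could be missing from the by-group table although the protocol collects SAEs over that period.
- If the window follows each person's own exposure, it closes soonest for those who stopped early, including those who stopped because of harm. A nominal 12-week control window has no such truncation.
- SAP 7.6 and section 8 give different rules. Two analysts following the same SAP could produce different harms tables, and the choice could be made after the data are seen.

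**Working it through.** **1. Arm size (used only for the illustration in step 4).** Inputs from SAP 4.3: d = 0.35, two-sided 5%, 90% power, 30% dropout. The normal approximation, n = 2(1.960 + 1.282)²/0.35², gives 172 per arm. The exact noncentral t calculation gives 173 (power 0.9008, against 0.8991 at 172), which matches the plan. 173/0.70 = 247.1, so 248 per arm and 496 in total, also as stated. The point below does not depend on the sample size.

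**2. Window lengths.**

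| Window | Derivation | Days | Share of 168 |
|---|---|---|---|
| Protocol 6.11.3.6.1, both arms | 24 × 7 | 168 | 100% |
| SAP 7.6, intervention, longest | 12 × 7 | 84 | 50% |
| SAP 7.6, intervention, fastest completion of all eight sessions | 7 gaps × 5 | 35 | 21% |
| SAP 7.6, intervention, never starts | no first exposure | none | – |
| SAP 7.6, usual care | no start event; 84 if the nominal schedule is used | undefined | – |

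The part of the nominal protocol period left out is 1 − 84/168 = 50% at least, and 1 − 35/168 = 79% for the fastest completer if treatment is taken to end at the last session. Someone who stops after fewer sessions could have a shorter window still. Follow-up may be completed within two weeks of the due date, so 168 days is nominal.

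**3. What the three statements in SAP 7.6 cover.** The window is attached to the first statement only. The SAE narrative and the SAE model carry no window, so section 8 can be read as governing them. For non-serious events, the window in the first statement is the only safety-specific analysis rule in the SAP.

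**4. Effect on counts (illustration).** The documents give no event rate. Assume a 24-week risk p that is equal in both arms, a constant hazard, and 248 per arm. The risk over L days is 1 − (1 − p)^(L/168).

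| Assumed p | Expected participants with an event per arm: 168 days | 84 days | 35 days | Apparent risk ratio, 35 v 84 days |
|---|---|---|---|---|
| 2% | 5.0 | 2.5 | 1.0 | 0.42 |
| 5% | 12.4 | 6.3 | 2.6 | 0.42 |
| 10% | 24.8 | 12.7 | 5.4 | 0.42 |

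Example at p = 5%: 248 × (1 − 0.95^0.5) = 6.3, and 248 × (1 − 0.95^(35/168)) = 2.6.

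- Both arms on weeks 0–12: ratio 1, with about half of the events lost.
- All intervention participants on 35 days and usual care on 84 (an extreme case): ratio about 0.42 with no true difference.
- Usual care counted to 168 days because routine support never stops: ratio about 0.21 (35 days) to 0.51 (84 days).

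**5. The SAE model (secondary).** In SAP 7.2 the random effects are site and therapist. Protocol 6.1.1 allows up to 20 sites and 36 therapists. Even over the full 24 weeks, the assumed intervention-arm counts of 5.0 to 24.8 come to 0.14 to 0.69 events per therapist, and usual care has no trial therapist. Protocol 6.11.3.1 says none were reported in the feasibility study. Non-convergence or separation is a realistic prospect, and SAP 7.6 names no fallback.

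**The case against.** **SAP 7.6 does not clearly discard late events.** A reader might infer that everything from weeks 12 to 24 is thrown away. The documents do not support that. The window qualifies one sentence, any SAE is to be described in full, the SAE model has no window, and section 8 includes data to study completion. This stands. The SAP contradicts itself, and what a literal reading loses is the late part of the by-group summary.

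**The arms need not be counted over different periods.** Protocol 6.4.2.2 gives usual care a nominal 12 weeks, and no text sets separate windows by arm. This also stands. Imbalance arises only if windows follow individual exposure or the two arms are closed differently. The milder reading still leaves out half of the period.

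**Unequal reporting does not establish a direction of bias.** Under Protocol 6.11.3.5.1, "the individual responsible for the care of the participant (Research Associate or trial therapist) must first assess whether or not the event is serious", and only one arm has a therapist, so a reader might conclude that the SAE comparison is biased against the intervention. That goes too far. The GP route in Protocol 6.11.3.1 and the follow-up calls in Protocol 6.6.1.2 apply to both arms, no detection rates are given, and a shorter intervention window would push the other way. The asymmetry is a limitation whose net direction is unknown.

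**Service-use admissions are not a ready substitute.** Protocol 6.11.3.1 excludes pre-existing disease, its exacerbation and newly detected physical conditions from SAEs. Admissions from the modified CSRI would be a different outcome, taken from follow-up forms for which 30% dropout is assumed.

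**The consequences are contained.** The GAD-7 analysis does not use this window. Live oversight does not either: SAEs go to the trials unit within one working day, and the monitoring committee is informed periodically. SAP 7.2 allows non-significant random effects to be dropped from the primary model, and SAP 7.5 allows documented changes. All this limits the seriousness of the point, but it does not settle which window the harms table should use.

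**Conclusion.** The point holds as a conflict that needs resolving before analysis. The only window that the SAP states specifically for safety data disagrees with Protocol 6.11.3.6.1, Protocol 6.11.3.1 and SAP section 8, and it cannot be applied to usual care or to participants who never start. Taken literally, it leaves at least 50% of the nominal 24-week period out of the by-group summary. That figure follows from the schedule alone. Whether the comparison is also unbalanced depends on how the undefined terms are applied. The risk ratios of about 0.21 to 0.51 are extremes under assumed, equal, constant risks, not predictions.

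The documents do not support saying that late SAEs are removed from the narrative or the model, that the arms will certainly be counted over different periods, or that the result will be biased in a known direction. Sparse data for the SAE model is a fair secondary concern, but it rests on assumed event rates.

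**What to change.** Reconcile the passages in SAP 7.6 by stating one analysis window: randomisation to the 24-week assessment or withdrawal, identical in both arms, with participants counted in their allocated arm. Apply it to the adverse event summary, the SAE listing and the SAE comparison, and show weeks 0–12 and 12–24 separately as well. Remove the wording based on first exposure and end of treatment.

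For SAEs, report the number of participants with an event by arm and a risk difference with an exact 95% confidence interval, either beside the logistic model with random effects or as its named fallback. State as a limitation that therapist reporting exists in one arm only and that the direction of the net bias is unknown.

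The cost is SAP wording. Protocol 6.11.3.6.1 already requires the SAE data for the whole window, and Protocol 6.11.3.1 already records non-serious incidents during the trial. The split at 12 weeks assumes that the forms carry event dates, which should be confirmed. The sample size and the primary analysis do not change.
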